8.3.2 Dose Selection

A FIH study was conducted in healthy subjects and concluded that a single bolus dose of E-WE thrombin up to 4 µg/kg was safe and generally well tolerated. Thus the 1.5 and 3 µg/kg doses were selected for this phase 2 study in order to provide adequate PD and efficacy characterization but still allowing a safety margin should the results differ in this population compared to healthy subjects. E-WE thrombin will be administered as a combination of a small bolus loading dose to induce rapid response but without significant systemic anticoagulation, and an infusion over 4 hours to prolong and sustain the duration of effect to cover the entire HD procedure.

8.3.3 Rationale for Pharmacodynamic Markers

The presumed half-life of active circulating E-WE thrombin in solution is very short (seconds to minutes) due to rapid binding to cell surface thrombin receptors. The active enzyme is not measurable in plasma using our enzyme capture assay at predicted human therapeutic doses. The Sponsor will use a PD biomarker (circulating APC-PCI complexes) as a surrogate for drug exposure.

8.4 Risk/Benefit

ESRD patients are often ill and are prone to a variety of AEs on or off HD, ranging, for example, from infections to hypertension to bleeding to thromboembolism to acute ischemic cardiovascular emergencies, even if they are apparently stable on chronic HD.

E-WE thrombin is a purified protein produced by recombinant DNA technology in a bacterial (*Escherichia coli*) cell culture system. All drugs, including heparins or recombinant proteins can occasionally and unpredictably evoke acute or chronic allergic reactions. Some ESRD patients develop chronic HD- and uremia-related moderate hemorrhagic diathesis or hemostasis impairment. The hemostatic safety of E-WE thrombin in the complex conditions of ESRD and chronic HD is not yet known. The safety monitoring practices employed by this protocol (i.e., AE questioning [including HD vascular access site reaction], physical examinations, bleeding time from the HD vascular access sites, vital sign measurements, 12-lead ECGs, clinical laboratory and coagulation tests) are adequate to protect the patients' safety and should detect all expected and unexpected TEAEs. In addition, the cohorts will be dosed in a sequential manner, starting with the lower dose level, Cohort 1.

There may be a higher risk of clots developing in the hemodialyzer during heparin-free HD. Should this occur, the site standard operating procedures will be followed to replace the clotted dialyzer and resume HD using a new cartridge under the supervision of the PI. It is important to note that replacement of the dialyzer cartridge is a safe procedure for the patient. While studies suggest that there is no risk of thromboembolic complications should this occur, complete clotting of the dialyzer circuit could result in up to ~228 mL of blood loss, and is usually prevented by replacing the dialyzer before complete occlusion.

As with all injectable recombinant or natural biologic products, subjects who receive these drug products may become immunized against the drug product. Subjects receiving E-WE thrombin may thus develop anti-drug antibodies (ADA), which may or may not neutralize the drug, or cross-react with and inhibit endogenous thrombin functions. While development of immunity and appearance of ADA in the circulation is not an AE as long as the ADA does not cross react with endogenous thrombin, the appearance of such antibodies will be monitored, as it may affect future tests and uses of the product, including future evaluation of repeat drug administration. Development of ADA that cross-react with the host's prothrombin/thrombin is a remote but existing possibility. All subjects will be assessed for the presence of antibodies to either E-WE thrombin or wildtype thrombin using validated assays.

There may be direct health benefits for study participants from receipt of study drug, some evaluated among the secondary outcome measures. E-WE thrombin has shown antithrombotic effects in nonclinical studies. Reduced thrombus accumulation on the dialyzer surface may potentially improve the efficiency of HD as well. An indirect health benefit for study participants enrolled in this study is the free medical tests received at screening and during the study.

9. STUDY OBJECTIVES AND ENDPOINTS

9.1 Study Objectives

The primary objective of this study is:

- To assess the safety and tolerability of a single dose of E-WE thrombin infused into the dialysis line during a 4-hour HD procedure in patients with ESRD.

The secondary objectives of this study are:

- To assess the PD of a single dose of E-WE thrombin infused into the dialysis line during a 4-hour HD procedure in patients with ESRD. APC-PCI will be used as a surrogate biomarker for drug exposure.
- To assess the efficacy of a single dose of E-WE thrombin infused into the dialysis line during a 4-hour HD procedure in patients with ESRD. Efficacy will be assessed by thrombus accumulation within the dialyzer cartridge (evaluated by visual inspection) and measurement of urea removed by 4 hours of dialysis (Kt/V and URR).

9.2 Study Endpoints

Primary outcome measures:

- The safety and tolerability of E-WE thrombin following active treatment will be evaluated versus pre-treatment and placebo by number and severity of AEs (including HD vascular access site reactions), physical examinations, bleeding time from the HD vascular access sites, vital sign measurements, 12-lead ECGs, clinical laboratory tests, and coagulation tests.

Secondary outcome measures:

- PD of E-WE thrombin will be measured by APC-PCI and plasma APC-PCI will act as a surrogate marker for E-WE thrombin drug exposure.
- Efficacy of antithrombotic activity will be evaluated by thrombus accumulation within the dialyzer cartridge (evaluated by visual inspection) after E-WE thrombin active treatment versus pre-treatment and placebo.
- Efficiency of HD will be assessed using BUN levels before and after dialysis to determine urea removed by 4 hours of dialysis (Kt/V and URR) after E-WE thrombin active treatment versus pre-treatment and placebo.

Other outcome measures:

- Development of antibodies to E-WE thrombin or WT thrombin after drug exposure.

10. INVESTIGATIONAL PLAN

10.1 Overall Study Design and Plan

This is a phase 2, randomized, double-blind, placebo-controlled, single-dose study of E-WE thrombin designed to evaluate the safety and efficacy at 2 dose levels administered to patients with ESRD during HD conducted at one study center in the US.

Patients will be enrolled in Cohort 1 or Cohort 2; cohorts will be dosed sequentially. Dosing of Cohort 2 will commence following completion of all study events for all patients in Cohort 1. Within each cohort, patients will be randomized to receive active drug or matching placebo as summarized below:

Table 1. Cohort and Treatment Randomization

Cohort	Treatment	Active:Placebo	Cohort Size
1	0.5 µg/kg bolus dose administered into the dialysis line immediately followed by a 0.25 µg/kg/hour continuous infusion dose into the dialysis line over 4 hours of E-WE thrombin or matching placebo, for a total dose of 1.5 µg/kg	2:1	12:6
2	1 µg/kg bolus dose administered into the dialysis line immediately followed by a 0.5 µg/kg/hour continuous infusion dose into the dialysis line over 4 hours of E-WE thrombin or matching placebo, for a total dose of 3 µg/kg	2:1	12:6

This study includes a screening period of 28 days prior to checking in to the CRU on Day -8. From Day -8 (8 days prior to dosing on Day 1) through Day 3, all patients will undergo HD 5 times and will be assessed for all scheduled procedures and endpoints before and after each HD session as per the Study Events Flow Chart ([Section 6](#)), using only one type of dialyzer cartridge for each patient.

On Day 1, prior to dosing, patients will undergo baseline measurements followed by initiation of a regular HD procedure, consistently using only one type of dialyzer cartridge for each patient. A single dose of E-WE thrombin or matching placebo will be administered into the dialysis line during the HD procedure. Patients will continue to undergo HD procedures and scheduled assessments from Day 1 through Day 3.

Study assessments will include AEs, including HD vascular access site (AV fistula or AV graft) reactions, physical examinations, vital sign measurements, 12-lead ECGs, clinical laboratory tests, coagulation tests, immunogenicity assessments, and PD blood sampling for APC-PCI and measurement of urea removed by 4 hours of dialysis to be performed throughout the study according to the Study Events Flow Chart ([Section 6](#)). On Days -7, -5, -2, 1, and 3, bleeding time from the HD vascular access sites on the AV fistula or AV graft (ladder or buttonhole technique) will be evaluated immediately at the end of the HD session. The dialyzer cartridge will be rinsed, visually inspected and graded against a

standardized visual assessment scale at the end of the HD procedure, and photographed on 4 sides.

Additionally, plasma and dialysate samples will be collected and sent to Sponsor along with the used and rinsed dialyzer cartridges for potential internal evaluation of plasma protein C, dialysate urea, and total protein accumulation within the dialyzer cartridge.

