7. ABBREVIATIONS

µg	Microgram
ADA	Anti-drug antibodies
AE	Adverse event
APC	Activated protein C
APC-PCI	Activated protein C with protein C inhibitor
aPTT	Activated partial thromboplastin time
ALT	Alanine aminotransferase
AST	Aspartate aminotransferase
AV	Arteriovenous
BMI	Body mass index
bpm	Beats per minute
BUN	Blood urea nitrogen
°C	Degrees Celsius
CFR	Code of Federal Regulations
cm	Centimeter
CRF	Case report form
CRU	Clinical Research Unit
CS	Clinically significant
ECG	Electrocardiogram
ESRD	End stage renal disease
FDA	Food and Drug Administration
FIH	First in human
FSH	Follicle-stimulating hormone
FU	Follow-up
g	Gram
GCP	Good clinical practice
GLP	Good laboratory practice
HBsAg	Hepatitis B surface antigen
hCG	Human chorionic gonadotropin
HCV	Hepatitis C virus

HD	Hemodialysis
HIT	Heparin-induced thrombocytopenia
HIV	Human immunodeficiency virus
IB	Investigator's brochure
ICF	Informed consent form
ICH	International Council on Harmonization
IND	Investigational New Drug
INR	International normalized ratio
IRB	Institutional Review Board
IV	Intravenous
kg	Kilogram
Kt/V	Ratio of volume of fluid completely cleared of urea
m ²	Meters squared
MedDRA®	Medical Dictionary for Regulatory Activities®
mg	Milligram
mL	Milliliter
mmHg	Millimeter of mercury
msec	Millisecond
n	Sample size
No.	Number
ng	Nanogram
NOAEL	No observed adverse effect level
oz.	Ounce
PD	Pharmacodynamic(s)
PI	Principal Investigator
PK	Pharmacokinetic(s)
PT	Prothrombin time
QA	Quality assurance
QTcF	Corrected QT interval using Fridericia's correction
SAE	Serious adverse event
SAP	Statistical analysis plan
SRC	Safety Review Committee

TEAE	Treatment-emergent adverse event
TT	Thrombin time
ULN	Upper limit of normal
URR	Urea reduction ratio
US	United States
USA	United States of America
WT	Wild type

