8.2.2.2 Pharmacodynamic Data

The APC-PCI was used as a surrogate biomarker for drug exposure.

Mean plasma APC-PCI concentration results following single IV doses of E-WE thrombin are presented in [Figure 1](#). Plasma APC-PCI was detectable in all subjects at the first sampling time point of 0.08 hour (5 minutes) post-injection and remained detectable throughout the entire sampling interval in all subjects up to 2 hours in the 0.5 µg/kg dose level group and up to 4 hours in the 1, 2 and 4 µg/kg dose level groups. Plasma concentrations of APC-PCI increased in a temporal and dose-dependent manner. All concentrations returned to baseline by 24 hours. Peak mean APC-PCI concentrations occurred at 0.5 hour (30 minutes) in all dose level groups. Ascending doses of E-WE thrombin increased the peak and overall

[figure not shown]
APC-PCI concentrations in a dose-proportional manner from the 0.5 to 2 $\mu\text{g}/\text{kg}$ dose levels, and slightly less than dose-proportional from the 2 to 4 $\mu\text{g}/\text{kg}$.

Figure 1. APC-PCI Complexes after E-WE Thrombin Administration in Healthy Subjects

Anticoagulation was verified by a temporal, dose-dependent increase in the aPTT, which returned to baseline by 4 hours (in the 0.5 and 1 $\mu\text{g}/\text{kg}$ groups) and by 24 hours (in the 2 and 4 $\mu\text{g}/\text{kg}$ groups). Administration of E-WE thrombin did not significantly impact prothrombin time (PT), platelets or fibrinogen levels (Figure 2). In the figure, laboratory reference ranges are shown with black dashed lines and clinically significant ranges are shown with red dashed lines.

Figure 2. Coagulation Parameters after E-WE Thrombin Administration in Healthy Subjects

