12. TREATMENTS

12.1 Treatments Administered

A separate pharmacy manual provided by the Sponsor will detail the preparation and treatment administration to be followed for this study.

E-WE thrombin will be supplied as a sterile, non-pyrogenic, preservative-free liquid for bolus and infusion.

E-WE thrombin will be supplied as 0.1 mg/mL, according to the planned dose ($\mu\text{g}/\text{kg}$) for each cohort, as noted below in [Table 2](#).

Matching placebo will be supplied as sterile formulation buffer for bolus and infusion.

Table 2. Investigational Products

Product	Description
Test	E-WE thrombin (0.1 mg/mL)
Placebo	Matching placebo for E-WE thrombin (16.2 mM sodium citrate, 3.8 mM citric acid, 150 mM sodium chloride, 0.1% polysorbate 80, at pH 6)

An unblinded pharmacist will be responsible for providing E-WE thrombin or matching placebo to the blinded study personnel for administration as per the randomization scheme.

Patients will be enrolled in Cohort 1 or Cohort 2. Within each cohort, patients will be randomized to active drug or matching placebo as summarized in [Table 1](#).

On Day 1, patients in each cohort will receive a single dose of E-WE thrombin or matching placebo as a bolus followed by an infusion into the dialysis line during a 4 hour HD procedure. Cohort 1 will be completed prior to initiation of Cohort 2.

Planned doses will be as follows:

Cohort 1: 0.5 $\mu\text{g}/\text{kg}$ bolus dose administered into the dialysis line immediately followed by a 0.25 $\mu\text{g}/\text{kg}/\text{hour}$ continuous infusion dose into the dialysis line over 4 hours of E-WE thrombin or matching placebo, for a total dose of 1.5 $\mu\text{g}/\text{kg}$.

Cohort 2: 1 $\mu\text{g}/\text{kg}$ bolus dose administered into the dialysis line immediately followed by a 0.5 $\mu\text{g}/\text{kg}/\text{hour}$ continuous infusion dose into the dialysis line over 4 hours of E-WE thrombin or matching placebo, for a total dose of 3 $\mu\text{g}/\text{kg}$.

Hour 0 will correspond to the beginning of E-WE thrombin bolus administration. The time of bolus administration and the times at which the infusion is started and stopped must be recorded.

The patient weight recorded at check-in will be used to calculate the study drug dose.

Should the need arise to change the infusion rate (i.e., due to an AE), changes to the infusion rate and the times at which those changes are made will be documented.

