12.3 Method of Assigning Patients to Treatment Groups

Each patient will be assigned a unique identification number upon screening. Patients who complete the study screening assessments and meet all the eligibility criteria will be assigned a unique randomization identification number at the time of dosing, different from the screening number, and will receive the corresponding product, according to a randomization scheme generated at Celerion.

Patients will be enrolled in Cohort 1 or Cohort 2 with Cohort 1 to be completed prior to the initiation of Cohort 2.

In each cohort, an attempt will be made to enroll at least 50% of females and at least 30% of a race/ethnic minority group. An attempt will also be made to approximately match key characteristics, including sex, average age, and weight between cohorts.

In each cohort, patients will be randomized to receive either E-WE thrombin or matching placebo maintaining a 2:1 ratio

If replacement patients are used, the replacement patient number will be 100 more than the original (e.g., Patient No. 101 will replace Patient No. 1).

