4.2 Preliminary Data and Interim Analysis

Celerion has not been contracted to complete any interim safety and PD analyses.

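### Cohort 2 starts at double the dose on completion of Cohort 1 alone, with no required review of Cohort 1 safety data as a group and no recorded decision

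*Protocol*

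**What the plan says.** Protocol 10.1: "Dosing of Cohort 2 will commence following completion of all study events for all patients in Cohort 1". The synopsis and SAP section 3 carry the same rule. Section 12.1 shortens it to "Cohort 1 will be completed prior to initiation of Cohort 2", and section 12.3 repeats it: "with Cohort 1 to be completed prior to the initiation of Cohort 2". Study events run to the Day 14 (± 2 days) follow-up, so that visit is part of the condition.

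Section 8.4 (Risk/Benefit) concedes that "The hemostatic safety of E-WE thrombin in the complex conditions of ESRD and chronic HD is not yet known" and, after listing the safety monitoring, adds as a further protection that "the cohorts will be dosed in a sequential manner, starting with the lower dose level, Cohort 1".

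Other oversight is as follows:
- **11.3:** reasons for discontinuing an individual patient.
- **13.2.8.2 and 13.2.8.3:** the investigator evaluates each AE and each clinically significant laboratory value.
- **13.2.8.4:** SAEs go to the sponsor within one working day.
- **12.4.2:** the blind may be broken for a safety interim analysis if the sponsor asks for one, or for everyone at a dose level if other patients appear to be at imminent risk.
- **15.2:** the sponsor may suspend or stop the study at any time, and the CRO or clinical unit may stop it for patient welfare.

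The protocol's abbreviation list contains "Safety Review Committee", but the term is not used in the text. SAP 4.2 says "Celerion has not been contracted to complete any interim safety and PD analyses".

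**The concern.** Dosing cohorts in order protects the second cohort only if somebody examines the first before the dose goes up. The protocol counts the ordering as a safety measure but leaves out the examination.

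Safety is the primary objective. The only human study described, in section 8.2.2, gave single boluses to healthy subjects, so the protocol reports no human data on an infusion and none in ESRD. The effect most worth looking for is hemostatic: somewhat longer access-site bleeding, or a coagulation shift at the end of the dosed session, across most treated patients. No single patient need have an AE, a clinically significant laboratory value or a reason to withdraw for that pattern to be present. Section 8.2.2.1 adds a specific gap: in the healthy-subject study, aPTT prolongation was not counted as an AE because it was expected. If the same convention is used here (an assumption), a review of AEs alone would not show it.

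At stake is the exposure of 12 further patients to twice the dose without a required look at the first 12.

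**Working it through.** **1. The plan's dose totals, and the step.** Inputs are from Table 1 in section 10.1; total = bolus + rate × 4 h.
- Cohort 1: 0.5 + 0.25 × 4 = 1.5 µg/kg. Cohort 2: 1 + 0.5 × 4 = 3 µg/kg. Both match the stated totals.
- Ratios: bolus 1/0.5 = 2; rate 0.5/0.25 = 2; total 3/1.5 = 2.

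**2. How large the step is** (sections 8.2.1.3, 8.2.2 and 8.3.2).
- Cohort 2 total against the highest healthy-subject bolus: 3/4 = 75%. Cohort 2 bolus against it: 1/4 = 25%.
- Infused share of the Cohort 2 dose: 2/3.
- Monkey NOAEL over the Cohort 2 total: 50/3 = 16.7.
- The healthy-subject doses (0.5, 1, 2, 4 µg/kg) also rose by doubling.

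**3. Does any other provision fill the gap?**

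| Provision | Looks at the cohort together? | Mandatory? | Tied to starting Cohort 2? |
|---|---|---|---|
| 11.3 early termination | No | At discretion, per patient | No |
| 13.2.8.2, 13.2.8.3 AE and laboratory review | No | Yes | No |
| 13.2.8.4 SAE reporting | No | Yes | No |
| 12.4.2 sponsor-requested safety interim analysis | Could | No | No |
| 12.4.2 unblinding of a dose level | Could | No; emergency with imminent risk to others | No |
| 15.2 suspension or termination | Could | No | No |

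No row is yes in all three columns, and the protocol's table of contents lists no escalation or safety-review section.

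**4. What a review would have to work with.** Assume all 18 are dosed and complete, with one bleeding time per session. The end of HD on Day 1 gives 18 bleeding times, 18 coagulation panels and 18 platelet counts, 12 of each on active drug. Each patient also has three pre-treatment sessions (Days -7, -5, -2) as their own comparison. SAP 7.5 and 7.7 add vital signs at 1 hour and an ECG at 0.5 hour. In healthy subjects there was a "temporal, dose-dependent increase in the aPTT, which returned to baseline by 4 hours" at 0.5 and 1 µg/kg, and by 24 hours at 2 and 4 µg/kg. If that timing carries over, Day 1 holds the direct effect, and Days 3 and 14 inform mainly on delayed effects.

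**5. What 12 active patients can show.** P(at least one event) = 1 − (1 − p)^12. For assumed true rates of 5%, 10% and 20% this is 46%, 72% and 93%. With 0 of 12, the one-sided 95% upper limit is 1 − 0.05^(1/12) = 22.1%.

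**6. Would a simple blinded count do as a decision rule?** Take the number of patients whose Day 1 bleeding time is strictly the longest of their four sessions. With no drug effect and exchangeable sessions, the chance per patient is at most 1/4. At most 18 × 0.25 = 4.5 are then expected, and for Binomial(18, 0.25), P(9 or more) = 0.019. Section 13.2.6 reads bleeding at 10 minutes and then every 5, so ties are likely and lower that chance. P(9 or more) when 12 active patients have the assumed rate and 6 placebo patients have the row's chance:

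| Placebo chance | Active 50% | Active 60% | Active 80% |
|---|---|---|---|
| 0.25 (no ties) | 0.31 | 0.54 | 0.93 |
| 0.10 (assumed) | 0.16 | 0.35 | 0.86 |
| 0.05 (assumed) | 0.11 | 0.29 | 0.83 |

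The top row is a best case. Ties would also make the active rates themselves harder to reach. The count misses moderate effects too often to carry a go/no-go decision.

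**The case against.** The strongest reply is that this is a gap in documentation, not in protection. It is a single-centre study with one dose per patient and confinement to Day 3. Trained staff, the same ones where possible, time the bleeding by hand (13.2.6). The investigator reviews and signs every CRF (15.6), and the investigator or sponsor may add safety evaluations (section 13). Waiting for every Day 14 visit leaves room for a review. The doses were chosen with a stated margin in case this population differs from healthy subjects (8.3.2).

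Much of that stands. The data and the opportunity for a review exist, and the margin keeps the point well short of a reason to stop. What it does not supply is a requirement: followed to the letter, the rule lets the dose double with no one having compared Day 1 with earlier sessions across patients. The margin rests on boluses in healthy subjects, and a review of Cohort 1 is how one would learn whether it holds in ESRD.

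Three stronger readings are tempting and are not supported:
- **That no review will take place.** SAP 4.2 says only that the CRO was not contracted for interim analyses. It does not rule out review by the investigator, medical monitor or sponsor, and a blinded clinical review is not an interim analysis.
- **That a safety committee was planned and dropped.** An unused abbreviation may be a template leftover and shows nothing either way. A separate charter cannot be excluded, though neither document refers to one.
- **That the step is unsafe.** Nothing in the documents shows this.

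**Conclusion.** The point holds as a gap in the escalation rule. Completion of Cohort 1 is the only stated condition for doubling bolus, rate and total dose. No provision requires a cohort-level look at safety or a recorded decision, and the provisions that could be used for one are optional and not linked to Cohort 2.

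The size is moderate, and the change is a cheap improvement. The conclusion needs no assumption about event rates or effect sizes. It rests on the current text of both documents and on no outside charter supplying the step; if one exists, a cross-reference settles the matter. The expectation that Day 1 carries most of the information does rest on carrying healthy-subject timing over to ESRD patients on an infusion. A review of 18 blinded patients would have limited sensitivity: no events among 12 treated would still be compatible with a true rate of about 22%.

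**What to change.** Amend section 10.1 and the matching sentences in the synopsis, 12.1, 12.3 and SAP section 3. Cohort 2 dosing should start only when (a) all Cohort 1 events are complete, and (b) the investigator, medical monitor and sponsor have made a documented blinded review of Cohort 1 and recorded a go/no-go decision.

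- **Content:** AEs, access-site bleeding times, coagulation and platelet results, vital signs and ECGs. Compare each patient's Day 1 values with their own pre-treatment values, and use Days 3 and 14 for delayed effects. The clinical team sets the thresholds. APC-PCI and antibody results should not be a condition, since those samples are shipped only at the end of the study (13.4.1, 13.5.1).
- **The longest-session count:** leave it out, or include it only as a supplementary check labelled best case.
- **Housekeeping:** use the abbreviation-list entry for this group or delete it.

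**Cost:** a protocol amendment approved by the sponsor, investigator and IRB (15.8), one meeting, and a short pause between cohorts. It needs no new samples or patients and no access to the randomization code. Two downsides remain. A pooled blinded review is coarse, because one third of the patients are on placebo. And aPTT may partly reveal treatment; giving the sponsor coagulation results only as pooled summaries limits this.
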